Appendix A: Inclusion/Exclusion Criteria Checklist.....	18

SCHEMA

LIST OF ABBREVIATIONS AND DEFINITION OF TERMS

AE	Adverse event
ALT	Alanine aminotransferase
AST	Asparagine aminotransferase
BIC	Bicarbonate
CBV	Cerebral blood volume
CNS	Central nervous system
CRF	Case report form
DCA	Dichloroacetate
DLT	Dose Limiting Toxicity
DNP	Dynamic nuclear polarization
DSMC	Data Safety Monitoring Committee
ECG	Electrocardiogram
EPA	Electron paramagnetic agent
FDA	Food and Drug Administration
GBM	Glioblastoma multiforme
GCP	Good clinical practices
GFR	Glomerular filtration rate
GGT	Gamma-glutamyltransferase
GLY	Glycolysis
IRB	Institutional Review Board
IV	Intravenous
LAC	Lactate
MRI	Magnetic resonance imaging
MRSI	Magnetic resonance spectroscopy imaging
MRS	Magnetic resonance spectroscopy
OXPHOS	Oxidative phosphorylation
PD	Protocol Director
PYR	pyruvate
SAE	Serious adverse event
SNR	Signal to noise ratio
SRC	Scientific Review Committee
T1	Time constant for magnetization decay
ULN	Upper limit of normal
VS	Vital signs

1. OBJECTIVES

1.1. Primary Objectives

To assess the safety of IV injection of hyperpolarized [1-¹³C]-pyruvate for MRI.

1.2. Exploratory Objectives

To assess the frequency and sensitivity with which lactate and bicarbonate signals can be detected in malignant brain tumors after IV injection of hyperpolarized [1-¹³C]-pyruvate.

2. BACKGROUND

2.1. Study Disease

Our ultimate goal is to develop a strategy to manage cancer as a chronic disease for which treatment can be calibrated according to the tumor's metabolic state. In particular, cancer cells, in addition to their high growth rate, universally demonstrate an abnormal metabolism characterized by an overproduction of lactate (via a process known as glycolysis [GLY]) relative to the more energy efficient conversion of glucose to carbon dioxide and water (oxidative phosphorylation [OXPHOS]). Originally described over 80 years ago by Otto Warburg, this altered metabolism, more recently termed *metabolic reprogramming* [1], is now viewed as a hallmark of cancer and appears linked to the need for carbon skeletons to produce biomass and is thus intimately tied to the ability of cancer cells to proliferate [2]. The novel clinical implication of these observations suggest that a potential anti-tumor strategy lies in reversing the "Warburg Effect" by forcing cancer cell metabolism away from GLY towards OXPHOS. Although this would not result in cell kill *per se*, it should result in stabilization of growth with minimal toxicity. Although a number of targets exist for which active drugs could be directed, a major obstacle towards taking this to the clinic has been the *inability to measure cancer metabolism in vivo*.

Using a rat model, we have developed magnetic resonance spectroscopic imaging (MRSI) of hyperpolarized [1-¹³C]-pyruvate as a noninvasive measure of lactate (Lac) and bicarbonate (Bic) production reflecting GLY and OXPHOS respectively [3], [4]. We now wish to translate this imaging technology to the clinic and demonstrate that these critical aspects of glucose metabolism can be measured in patients with glioma. A hyperpolarizer that can be used clinically has been purchased and is now ready to be utilized. We have funds in which to test 15 subjects and would like to perform a pilot test to confirm two necessary aspects of our hypothesis: (i) determining that our methods for polarizing [1-¹³C]-pyruvate are safe for patient use; and (ii) evaluating if and how frequently we can detect lactate and bicarbonate signaling within brain tumor tissue.

2.2. Study Agent/Device/Imaging procedure

Dynamic nuclear polarization (DNP) magnetic resonance spectroscopic imaging (MRSI) is based on the transfer of polarization from the electron spins of paramagnetic centers embedded in a glassy frozen solution to neighboring nuclear spins through dipolar interactions, thus driving nuclei temporarily into a significant redistribution of the ordinary populations of energy levels [5]. These spin states are not stable in the sense that the induced massive spin polarization decays during a relatively short period but within this period allows one to follow a nucleus (usually carbon or nitrogen) as it is processed by a tissue. The absence of ionizing radiation and convenient integration with standard MRI imaging of hyperpolarized nuclei therefore offers the prospect of monitoring tumor metabolism noninvasively, the potential value of which depends on three factors: (i) the T1 signal needs to be sufficiently long so that enough material is preserved after injection to measure; (ii) the metabolic pathway itself must be sufficiently rapid so that the fate of the tracer can be measured; and (iii) the process must be relevant to tumor biology [6].

[1-¹³C]-pyruvate is currently the tracer for which the most preclinical and clinical experience exists. Pyruvate (Pyr) is situated at a hub of the glucose utilization pathway where it can be reduced to lactate, amidated to alanine or catalyzed to acetyl CoA and CO₂. Although an issue existed early in its development as to whether it could cross the blood brain barrier fast enough to allow imaging in brain tumors without disruption, unequivocal imaging of brain tumor metabolism of hyperpolarized [1-¹³C]-pyruvate in brain has been demonstrated [4].

Signal to noise (SNR) ratios are particularly strong for visualizing lactate (Lac), on which most studies to date have focused. Using this technology, it has been possible to show lactate dehydrogenase catalyzed interconversion of label between Pyr and Lac in several tumor types including GBM and that changes occur in the rate of labeling with treatment [4], [7]-[9]. Furthermore, it has also been demonstrated that an increased conversion of Pyr conversion to alanine is an early feature of experimental myc-driven hepatic tumors [10].

Based on numerous previous reports, tracing Pyr fate into the mitochondria has been more challenging and there have been numerous reports noting that imaging both lactate and bicarbonate (Bic) is difficult, especially in brain tumor [11], [12], creating barriers for using this imaging modality to explore the question of whether forcing OXPHOS slows cancer growth.

We recently overcame this hurdle through optimization of the acquisition protocol for spiral chemical shift imaging so as to be able to measure both lactate and bicarbonate in transplanted C6 glioma. Furthermore, we were able to demonstrate a consistent and marked decrease in the ratio of Lac/Bic acutely after the administration of DCA [8], substantiating at least that change in Pyr flux is occurring so that more substrate is directed into the mitochondria (since that is where Bic is generated).

This technology has been recently applied to clinical populations. The first-in-man Phase I trial examined a cohort of prostate cancer patients. It demonstrated the safety of administering 250 mM hyperpolarized [1-¹³C]-pyruvate up to doses of 0.43 mL/kg body weight and that images could be acquired that demonstrated conversion of hyperpolarized pyruvate to lactate in regions of biopsy-proven tumor [13]. Since these experiments were reported from UCSF, this technology has become available for clinical study at Memorial Sloan Kettering Cancer Center, University of Texas at Southwestern (UTSW), Cambridge University, Oxford University, University of Toronto, and several other centers (including ours) are gearing up for study.

2.3. Clinicaltrials.gov

This study is submitted to IND-[REDACTED] for the IV injection of [1-¹³C]-pyruvate, and will include submission of this protocol.

For clinicaltrials.gov compliance: This is a phase 0 (early phase 1), but relies in part on NIH funding so is required to register on clinicaltrials.gov and report results. For Clinicaltrials.gov results reporting, the following outcome measures will be used:

Primary Outcome Measure

- Title: Safety of hyperpolarized [1-¹³C]-pyruvate injection
- Time Frame: Up to Day 4
- Description: Results will be reported as the number of Grade 2 or higher adverse events judged by the investigator to be clinically significant AND related/possibly-related to hyperpolarized [1-¹³C]-pyruvate injection across all subjects administered study agent.

Exploratory Outcome Measure

- Title: Feasibility of Lactate and Bicarbonate signal detection
- Time Frame: Up to 4 days
- Description: Results will be reported as the percentage of subjects with CNS malignancy administered study agent and imaged who show ^{13}C MR signal detection above background noise level, reported separately for lactate and bicarbonate signals.

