7. ADVERSE EVENTS AND REPORTING PROCEDURES

7.1. Potential Adverse Events

In the original Phase I studies with [1-¹³C]-pyruvate, no dose-limiting toxicities or toxicities deemed to be clinically significant were noted [13]. We will consider any Grade 2 or higher toxicity judged related or possibly-related to [1-¹³C]-pyruvate as significant (excluding asymptomatic lab abnormalities).

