9. MEASUREMENTS

9.1. Primary and Exploratory Outcome measures

Primary Outcome Measure: This is a pilot study which will allow us to develop a novel MRS technique for clinical application. Our primary measurement will be safety of [1-¹³C]-pyruvate IV injection defined as the absence of Grade 2 toxicity (except for asymptomatic lab increases).

Exploratory Outcome Measure: Detection of lactate and bicarbonate production in tumor and normal brain tissue, defined as the frequency of ¹³C MR signal detection above background noise level of both lactate and bicarbonate in all tumors screened.

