10. STATISTICAL CONSIDERATIONS

10.1. Statistical Design

This pilot study seeks to demonstrate safety of the [1-¹³C]-pyruvate IV injection as well as the ability to detect lactate and bicarbonate spectra. Safety will be defined as the absence of Grade 2 toxicity (except for asymptomatic laboratory abnormalities).

Another goal is an assessment of whether lactate and bicarbonate spectra can be detected in tumor. Three answers are anticipated. Either there will be bicarbonate spectra detected in all, some or none. Our experimental data suggests that we should be able to see it in all enhancing areas, although the technical differences between experimental and clinical machines does not guarantee this outcome.

5 healthy volunteers and 10 patients with CNS malignancies will be assessed, which is the maximum that our budget will allow. These results will then be used to properly formulate a more formal experiment that will subsequently be submitted.

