10.4. Descriptive Statistics and Exploratory Data Analysis

N/A

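### The primary safety result is planned as a pooled event count with no number of affected subjects and no interval, while absence of Grade 2 toxicity in 15 people is to count as safety

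*Combined protocol and SAP*

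**What the plan says.** The primary objective in section 1.1 is modest: "To assess the safety of IV injection of hyperpolarized" pyruvate for MRI.

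Section 2.3 fixes the primary outcome for registry reporting: "Results will be reported as the number of Grade 2 or higher adverse events judged by the investigator". Two conditions then narrow which events count: "to be clinically significant AND related/possibly-related to hyperpolarized", the agent being the injected pyruvate. The count is pooled over everyone dosed in both arms. The exploratory outcome in the same section is, by contrast, a percentage of subjects.

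Section 7.1 defines what counts as significant: "We will consider any Grade 2 or higher toxicity judged related or possibly-related to" pyruvate, with asymptomatic laboratory abnormalities left out.

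Section 9.1 describes the primary measurement as safety, "defined as the absence of Grade 2 toxicity (except for asymptomatic lab increases"). Section 10.1 opens with "This pilot study seeks to demonstrate safety of the" injection and continues: "Safety will be defined as the absence of Grade 2 toxicity (except for asymptomatic laboratory abnormalities").

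Sections 10.4 (descriptive statistics) and 10.5 (primary analysis) contain only N/A. Section 10.6 sets the sample at 5 healthy volunteers and 10 patients on budget grounds. No section gives a tolerated toxicity rate, a confidence level or a subject-level summary of safety.

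**The concern.** Two gaps follow from the planned summary, and they arise in different outcomes.

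If no dosed subject has a Grade 2 or higher toxicity, the criterion in 9.1 and 10.1 is satisfied and the study has done what 10.1 sets out to do. Nothing in the plan then requires a statement of how high the true rate could still be. With 15 subjects, that is the most informative thing the safety data can offer.

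If two or more qualifying events occur, the count alone does not say whether one person or several were affected. Pooling also leaves the split between volunteers and patients unspecified.

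In addition, the sections do not agree on which events count, so the same data could give zero under 2.3 and still fail 10.1 read literally.

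Section 10.1 says the results will be used to formulate a more formal experiment, and 10.8 places the next study in GBM patients. Anyone planning that study could reasonably want the proportion of people affected, particularly patients, and its upper limit.

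**Working it through.** **Inputs.** Subjects: 5 + 10 = 15 (sections 2.6, 10.1 and 10.6), which reproduces the stated total. That total comes from the budget, so there is no precision or power figure to reproduce. The documents give no confidence level; two-sided 95% is assumed here. The pooled figures also assume that all 15 are dosed and that one rate applies to both arms.

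**Zero affected subjects.** The exact (Clopper-Pearson) two-sided 95% upper limit for 0/n is 1 − 0.025^(1/n).

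| Subjects | Calculation | Upper limit |
|---|---|---|
| All dosed, 0/15 | 1 − 0.025^(1/15) | 21.8% |
| Arm 2 (patients), 0/10 | 1 − 0.025^(1/10) | 30.8% |
| Arm 1 (volunteers), 0/5 | 1 − 0.025^(1/5) | 52.2% |

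Check: (1 − 0.218)^15 = 2.5%, as it should be. A one-sided 95% limit for 0/15 is 1 − 0.05^(1/15) = 18.1%; the Wilson limit is 20.4% and the rule of three gives 3/15 = 20.0%. The message does not depend on the method.

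Section 4.3 leaves the use of pyruvate to the Protocol Director's discretion, so fewer than 15 may be dosed. The limit is then higher: 0/14, 23.2%; 0/13, 24.7%; 0/12, 26.5%.

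**How often zero would be seen.** With a common true rate p, the chance that none of 15 is affected is (1 − p)^15. All rates here are assumptions.

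- p = 5%: 46.3%
- p = 10%: 20.6%
- p = 20%: 3.5%

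If volunteers are assumed to carry no risk, the chance is (1 − p)^10 for the patients: 10.7% at 20% and 5.6% at 25%.

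**Two events.** A reported count of 2 fits either of these results (limits from beta quantiles):

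- one subject affected: 1/15 = 6.7%, 95% CI 0.2% to 31.9%
- two subjects affected: 2/15 = 13.3%, 95% CI 1.7% to 40.5%

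**The numerator, section by section.**

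| Section | Grade | Attribution | Clinical significance | Asymptomatic laboratory changes |
|---|---|---|---|---|
| 2.3 | 2 or higher | related or possibly related | a further investigator judgement | not mentioned |
| 7.1 | 2 or higher | related or possibly related | follows from grade and attribution | excluded |
| 9.1, 10.1 | 2, with no mention of higher grades | none stated | none stated | excluded |

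A Grade 2 toxicity judged unrelated would not count under 2.3 but would breach 10.1 as worded. A related Grade 2 toxicity that the investigator did not judge clinically significant would be significant under 7.1 but not counted under 2.3.

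**The case against.** The strongest defence is that this is a budget-limited phase 0 pilot that states no hypothesis test, tolerated rate or confidence level, so the 21.8% is a reader's calculation and not a planning error. That is right. The plan contains no wrong number, and nothing here shows that 15 subjects is the wrong number for a pilot. But a small sample makes an interval more useful, and the difficulty comes from pairing that sample with an aim to demonstrate safety.

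A second defence is that 2.3 governs a registry entry and does not rule out other summaries. Adverse events go on case report forms under 7.2, so affected subjects can be counted, and anyone given the number dosed can work out a limit. This also stands in part. A reader might infer that the plan conceals or loses the number of affected subjects; the documents do not support that. The number is unspecified in the reported result, and only when there are two or more events. With none, or with one, the count already determines it. A second dose-limiting event would also pause enrollment for a safety review under 7.1.1, although that is not a reporting rule.

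A third defence is prior experience: section 7.1 says the original Phase I studies found no dose-limiting or clinically significant toxicity, and 4.3 calls such an event unlikely. That makes zero the likely outcome, which is exactly where a stated limit is missing. The Phase I cohort described in section 2.2 had prostate cancer, and this study makes safety its own primary objective.

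Finally, neither 10.1 nor 10.8 says that a toxicity rate is a design input for the next study. Its use there is an inference.

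**Conclusion.** The concern holds as a gap in the planned analysis and reporting, and should be corrected. As written, the plan would allow a result with no Grade 2 or higher toxicity to stand as demonstrated safety while the true rate could be as high as 21.8% overall or 30.8% in patients. With two or more events, the specified count would not separate one affected subject from several. The limits rest on a two-sided 95% level, full dosing of the arms concerned and, for the pooled figure, one common rate; none of these comes from the documents.

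A reader might go further and infer that a zero count under 2.3 by itself satisfies the protocol's definition of safety. The documents do not support that: 2.3 counts only related, clinically significant events, while 9.1 and 10.1 state neither condition. The definition is met when no Grade 2 or higher toxicity of any attribution occurs, asymptomatic laboratory changes aside. A zero under 2.3 is a weaker statement.

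**What to change.** 1. Reconcile 2.3, 7.1, 9.1 and 10.1 to a single numerator. The sponsor should choose it and state grade, attribution, the role of the clinical-significance judgement and the treatment of asymptomatic laboratory changes. Dropping or keeping that separate judgement changes the primary outcome, so it should be a deliberate decision.
2. In 2.3 and 10.5, report the number and percentage of dosed subjects with at least one qualifying event, with exact (Clopper-Pearson) 95% confidence intervals, overall and by arm. Use the number actually dosed as the denominator and keep the event count as supporting data.
3. In 10.1, replace the aim of demonstrating safety with estimation, in line with 1.1, and state the upper limit. For example: 0/15 affected, two-sided 95% upper confidence limit 21.8%.
4. If enrollment was paused under 7.1.1 or more than one dose was used under 4.3, say so beside the interval and treat it as descriptive, because a fixed-size, single-dose binomial model no longer strictly applies.

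The cost is a less favourable safety statement, very wide by-arm intervals (the volunteer arm could show an upper limit of 52.2% with nobody affected), and a protocol amendment through the approvals in section 8.1. No further subjects or data are needed, and no clinical rule needs to change.

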2.4. Rationale

See Section 2.1

2.5. Preliminary results

The proposed study will be the first time at Stanford where this technology will be used in humans. Prior use in cancer imaging, conducted at UCSF, is described in the Investigator's Brochure.

2.6. Study Design

This is an open-label, two-armed study of 5 healthy volunteers and 10 patients with known CNS malignancy.

- Arm 1: n = 5 healthy volunteers
- Arm 2: n = 10 patients with known CNS malignancy

3. PARTICIPANT SELECTION AND ENROLLMENT PROCEDURES

3.1. Inclusion Criteria

- 3.1.1.** (Arm 2 patients with known CNS malignancy only) Patients with a known diagnosis of CNS malignancy, including metastases, with known enhancement on MR who are otherwise eligible to undergo MRI.
- 3.1.2.** At least 18 years old.
- 3.1.3.** eGFR $> 30 \text{ ml/min}$.
- 3.1.4.** (Arm 2 patients with known CNS malignancy only) No allergy to gadolinium.
- 3.1.5.** Ability to understand and the willingness to sign a written informed consent document.

3.2. Exclusion Criteria

- 3.2.1.** Refusal to have an IV placed for injection.
- 3.2.2.** Acute major illness (e.g., unstable angina, etc.) or other condition that makes participation unsafe, per the investigator's judgement.
- 3.2.3.** Total Bilirubin $> 1.5 \times \text{ULN}$; AST/ALT $> 2.5 \times \text{ULN}$; GGT $> 2.5 \times \text{ULN}$.
- 3.2.4.** Pregnant or breast-feeding.
- 3.2.5.** Cardiovascular risk, including:
 - Poorly controlled hypertension, defined as either systolic > 170 or diastolic > 110 .
 - Congestive heart failure
 - Myocardial infarction within the past year
 - QT prolongation, defined as pretreatment QTc $> 440 \text{ msec}$ in males or $> 460 \text{ msec}$ in females
- 3.2.6.** (Arm 1 Healthy volunteers only) Undergoing active treatment for malignancy

3.3. Informed Consent Process

All participants must be provided a consent form describing the study with sufficient information for participants to make an informed decision regarding their participation. Participants must sign the IRB approved informed consent prior to participation in any study specific procedure. The participant must receive a copy of the signed and dated consent document. The original signed copy of the consent document must be retained in the medical record or research file.

3.4. Study Timeline

3.4.1. Primary Completion

The study will reach primary completion once the last subject undergoes Day 2 safety evaluations.

3.4.2. Study Completion

We estimate that this study will take one year from first subject enrollment to complete.

4. IMAGING AGENT/DEVICE/PROCEDURE INFORMATION

4.1. Hyperpolarized [1-¹³C]-Pyruvate

¹³C is a stable non-radioactive isotope of carbon. [1-¹³C]-pyruvate has exactly the same chemical characteristics as pyruvate. In [1-¹³C]-pyruvate, the C-1 carbonyl has been enriched with ¹³C-nuclei, which has a magnetic moment and can be hyperpolarized by DNP in the presence of an electron paramagnetic agent (EPA), i.e., AH111501 sodium salt (a stable trityl radical). Although [1-¹³C]-pyruvate has the same chemical characteristics as unlabeled pyruvate and is metabolized the same way, the fact that it can be hyperpolarized means that MRSI can be used to rapidly detect the hyperpolarized ¹³C-label in [1-¹³C]-pyruvate and its metabolic products.

Hyperpolarized [1-¹³C]-pyruvate will be prepared by qualified staff at the Lucas Center under aseptic GMP/GLP conditions using a DNP polarizer (SpinLab, GE Healthcare). The imaging agent will be administered by IV injection at a rate of 5 ml/sec followed by a 20 ml saline flush at 5 ml/sec (on average 30-40 seconds). The formulation procedures are detailed in the current Investigator's Brochure (IB).

4.2. Dissolution DNP MRSI

Hyperpolarized [1-¹³C]-pyruvate will be injected at a dosage of 0.43 ± 0.05 mL/kg body weight (concentration of 250 mM), the maximum safely administered dose attained in the Phase I study [13]. After hyperpolarization in the SpinLab polarizer, a syringe is automatically filled. The quality control module of the SpinLab measures the pyruvate concentration, volume, temperature, pH, polarization, and removal of the EPA in the syringe. A quality control assessment is then performed to ensure all parameters are reached, after which the syringe is released by the protocol director and immediately passed to a nurse or radiology technician for initiation of injection.

The overall imaging protocol will consist of 1) standard non-contrast clinical collection setup for brain imaging (~45 min), 2) hyperpolarized [1-¹³C]-pyruvate MRSI (single- or multi-slice acquisition, ~3-min acquisition), and 3) standard clinical brain gadolinium-enhanced MRI (~10min).

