4.3. Dose Modification

The starting dose of [1-¹³C]-pyruvate will be 0.43 ± 0.05 mL/kg body weight (250 mM [1-¹³C]-pyruvate). If we encounter a DLT at this dose (which seems unlikely since it has been well tolerated in safety studies elsewhere), we will decrease dose to 0.28 mL/kg.

The choice whether or not to use the [1-¹³C]-pyruvate and/or gadolinium MRI contrast agent is made at Protocol Director's discretion. If the investigator chooses to forego gadolinium contrast (due to concerns of gadolinium accumulation or other concerns), the second MRI brain scan may be skipped.

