5. STUDY PROCEDURES

Healthy volunteers (Arm 1 of the study) will be recruited via an IRB-approved e-mail that refers them to the clinical research coordinator or research team. Eligible patients for arm 2 will be invited to participate at any time during their course of CNS malignancy treatment. Generally, arm 2 patients will be recruited during a regular clinic visit.

If the patient signs the informed consent form and agrees to participate, the following screening procedures will be performed within 14 days prior to Day 1:

- Collect demographics
- Measure vital signs (heart rate, temperature, blood pressure), height and weight
- Serum chemistry blood test
- Serum pregnancy test, if woman of childbearing potential
- Electrocardiogram (ECG)

On Day 1, MRI and MRSI will be performed in the Richard M. Lucas Center for Imaging at Stanford University. Production of hyperpolarized [1-¹³C]-pyruvate will be coordinated with imaging schedule such that MRSI begins within 1 minute of hyperpolarized [1-¹³C]-pyruvate administration. Each subject will undergo the following procedures:

- Measure vital signs
- MRI scan of brain, 45 min acquisition time using standard non-contrast clinical brain collection setup
- Administration of hyperpolarized [1-¹³C]-pyruvate (250 mM, 0.43 ± 0.05 mL/kg body weight) IV injection at a rate of 5 mL/sec followed by a 20 mL saline flush at 5 mL/sec (on average 30-40 seconds)
- MRSI scan of brain, 3 min acquisition on a 3T MRI scanner equipped with both 1HF and ¹³C RF coils.
- MRI scan of brain, 10 min acquisition time using standard Gadolinium-enhanced contrast clinical brain collection. Gadolinium contrast agent may or may not be administered at the discretion of the Protocol Director. Gadolinium will not be used for Arm 1 Healthy Volunteers.
- Within 10 min after the conclusion of image collection:
 - Measure vital signs
 - Collect any adverse events and monitor injection site
- At least once more 20-45 minutes after the conclusion of image collection:
 - Measure vital signs
 - Collect any adverse events and monitor injection site
- 1 to 5 hours post pyruvate administration:
 - Measure vital signs
 - ECG
 - Collect any adverse events and monitor injection site

Between Day 2 and 4, subjects will be contacted by phone or at an in-person clinic visit to collect any adverse events.

Once initial imaging is completed, patients will be followed as expected by standard of care. Patients are free to enroll in other studies.

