10.6. Sample Size

Our budget allows 5 healthy volunteers and 10 patients with CNS malignancies for a total of 15 subjects. This number will allow us to accrue enough data to better understand lactate and bicarbonate detectability and safety.

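### The permitted dose range reaches 0.48 mL/kg, 11.6% above the highest dose for which the protocol itself quotes human safety support (0.43 mL/kg), and the tolerance is not explained

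*Combined protocol and SAP*

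**What the plan says.** The protocol describes the dose in four places.

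- **Section 2.2** (Study Agent/Device/Imaging procedure) summarises the first-in-man Phase I trial in prostate cancer and says that it showed the 250 mM agent to be safe "up to doses of 0.43 mL/kg body weight". No tolerance is attached.
- **Section 4.2** (Dissolution DNP MRSI) sets the dose for this trial as "0.43 ± 0.05 mL/kg body weight (concentration of 250 mM), the maximum safely administered dose attained in the Phase I study", citing the same reference as Section 2.2.
- **Section 4.3** (Dose Modification) gives the starting dose with the same tolerance: "pyruvate will be 0.43 ± 0.05 mL/kg body weight (250 mM". It considers a dose-limiting toxicity at this dose to be an event "which seems unlikely since it has been well tolerated in safety studies elsewhere", without naming those studies or their dose levels.
- **Section 5** (Study Procedures) repeats it for Day 1: "250 mM, 0.43 ± 0.05 mL/kg body weight) IV injection at a rate of 5 mL/sec". The Day 1 list applies to every subject, so it covers the 5 healthy volunteers as well as the 10 patients.

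Section 4.2 also describes the release of each syringe. The polarizer's quality control module measures concentration and volume, among other things, and "A quality control assessment is then performed to ensure all parameters are reached". No upper limit in mL/kg is given as a release condition.

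**The concern.** A range that extends above 0.43 mL/kg is presented as the maximum that Phase I reached safely, while Section 2.2 puts that maximum at 0.43 mL/kg. A team that follows the plan exactly can give more than the only human dose level that the protocol supports with a number. That would involve no deviation, and it applies to healthy volunteers too.

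This bears on the main purpose of the trial. Safety is the sole primary objective (Section 1.1), and Section 2.5 says this is the site's first human use of the technology. The primary outcome in Section 2.3 is a count of qualifying adverse events over everyone dosed, and it takes no account of the dose each subject received. Sections 10.4 and 10.5 (descriptive statistics and primary analysis) are marked not applicable, so no planned summary describes exposure. With 15 subjects, a reader of the results could not tell which exposures the safety finding covers, or whether any event fell above the level for which support is quoted.

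**Working it through.** The plan derives no figure from the tolerance, so there is nothing to reproduce. The sample size is set by budget and plays no part here. The check is direct arithmetic on the stated dose.

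**Inputs**

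| Input | Value | Source |
|---|---|---|
| Nominal dose | 0.43 mL/kg | Sections 4.2, 4.3, 5 |
| Tolerance | ± 0.05 mL/kg | Sections 4.2, 4.3, 5 |
| Nominal concentration | 250 mM = 0.250 mmol/mL | Sections 2.2, 4.2, 4.3, 5 |
| Highest dose with quoted safety support | 0.43 mL/kg, no tolerance | Section 2.2 |
| Body weights | 50, 70, 100 kg | Assumed for illustration; the documents give none |

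**Step 1: permitted range.** Lower end 0.43 − 0.05 = 0.38 mL/kg. Upper end 0.43 + 0.05 = 0.48 mL/kg.

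**Step 2: relative excess at the upper end.** 0.48/0.43 − 1 = 0.05/0.43 = 11.6%.

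**Step 3: molar dose at the nominal concentration.** 0.43 × 0.250 = 0.1075 mmol/kg. 0.48 × 0.250 = 0.120 mmol/kg.

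**Step 4: volume above 0.43 mL/kg that remains compliant.**

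| Weight (assumed) | At 0.43 mL/kg | At 0.48 mL/kg | Difference |
|---|---|---|---|
| 50 kg | 21.5 mL | 24.0 mL | 2.5 mL |
| 70 kg | 30.1 mL | 33.6 mL | 3.5 mL |
| 100 kg | 43.0 mL | 48.0 mL | 5.0 mL |

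**Step 5: search for text that would close the gap.** Three kinds of statement would do so: a cap on delivered dose at 0.43 mL/kg, an explanation of the ± 0.05 as filling or measurement error, or a human dose level above 0.43 mL/kg with safety data. None appears. Section 4.3 refers to good tolerability elsewhere but gives no dose. Section 7.1 relies again on the same Phase I reference and also gives no dose.

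**The case against.** The strongest reply is that 0.43 mL/kg is a nominal dose and ± 0.05 is a delivery tolerance. Section 4.2 attaches its description of the Phase I maximum to the whole expression, tolerance included, and Section 2.2 may simply give the same dose level by its nominal value. The Phase I study may have worked to the same tolerance. Only its report or the Investigator's Brochure could settle that, and neither is available here. This stands as a limit on the point. A reader might infer that Section 4.2's statement is false for doses above 0.43 mL/kg, but the documents show only that it does not match Section 2.2 and that the tolerance is unexplained.

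A reader might also infer that 0.43 mL/kg is a safety ceiling and that exceeding it is dangerous. The documents do not say so. They describe it as the highest dose given, and Section 7.1 reports no dose-limiting or clinically significant toxicity in the original Phase I work.

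Third, Section 4.3 offers a second justification, tolerability elsewhere, and applies it to the dose written with its tolerance. It does count as stated support. Without a dose level or a citation, however, it does not show that the upper end has been given.

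Fourth, safeguards exist. Volume and concentration are checked and each syringe is released by the protocol director (Section 4.2). Section 4.3 provides for dose reduction after a dose-limiting toxicity, and Section 7.1.1 pauses enrolment after two. These temper the severity, but none of them limits mL/kg.

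Finally, it is tempting to say that the result will be presented as safety at 0.43 mL/kg. No section says that: the objective and the outcome definitions refer to the injection and name no dose. The full 0.38 to 0.48 mL/kg spread (0.48/0.38 = 1.26, or 26%) is likewise no measure of how far 0.43 mL/kg can be exceeded.

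**Conclusion.** The point holds as an inconsistency between the permitted dose range and its quantified justification. Compliant dosing can reach 0.48 mL/kg, 11.6% above the 0.43 mL/kg for which Section 2.2 reports Phase I safety. At the nominal concentration this is 0.120 against 0.1075 mmol/kg.

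The conclusion assumes that the ± 0.05 means what it says, namely that any delivered dose within it is acceptable, and that the protocol text is the whole of the available justification. The molar figures also assume exactly 250 mM, and the volumes depend on the assumed weights. If the Phase I report or the Investigator's Brochure documents the same tolerance or higher exposures, the gap is one of wording and citation. It is a gap in stated support and says nothing about harm at 0.48 mL/kg.

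Severity is moderate, because safety is the only primary objective and healthy volunteers are included. Confidence is medium, because the deciding sources are outside the file.

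**What to change.** 1. Reconcile Sections 2.2, 4.2, 4.3 and 5 so that the permitted range and the stated maximum with safety support agree. State what the ± 0.05 represents (for example filling, measurement or prescribing tolerance) and cite the source that supports its upper end. Which figure is right is for the sponsor to determine.
2. For each subject, derive the actual dose as mL/kg = injected volume / screening weight, and mmol/kg = mL/kg × measured concentration in mmol/mL. Concentration and syringe volume are already measured at release, and weight is taken at screening. The case report forms are not in the file, so confirm that the injected volume is recorded.
3. Report these exposures beside the primary safety result, for instance as a listing of all 15 subjects with any qualifying event, and identify any subject above 0.43 mL/kg.

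The cost is a protocol wording change, a dose derivation and one short listing, with no new patient procedure. The main downside is that the sponsor may have to re-justify the tolerance if the cited source does not cover it.
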